## **Reporting of Adverse Events or Unanticipated Problems involving Risk to Participants or Others**

Adverse event identification will be the responsibility of each member of the research team and to report same to one of the trauma surgeons, [name]; [name]; and [name]. Specifically, [name] will be responsible for reporting promptly to the IRB office.

### **Study Withdrawal/Discontinuation**

If at any time during the course of the patient's treatment or data collection, the patient decides to withdraw from the study they may do so without any consequence. If the patient decides to withdraw after consent is given they may do so and will not be included in the study.

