## Rationale and Specific Aims

The primary objective of this study is to determine whether a patient with a tibial plateau fracture (non-displaced, displaced, depression type) will have decreased pain and narcotic analgesia requirements following an intra-articular injection of local anesthetic and aspiration of the knee. In order to determine whether this institution has an appropriate volume of tibial plateau fractures to adequately perform such a trial, we have reviewed our volume of tibial plateau fractures and have determined we have an adequate volume to conduct such a study. The primary outcome of the study could potentially guide future management of tibial plateau fractures at this institution and potentially systemically.

- a) Specific Aim 1: Examine the effect of hemarthrosis aspiration and intra-articular bupivacaine injection on recorded Numerical Rating Scale (NRS) pain scores for patients with tibial plateau fractures in the first 24 hours following injury.**
- Working Hypothesis: Hemarthrosis aspiration and intra-articular bupivacaine injection will significantly decrease subjective pain scores in the early post-injury period.*

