- This study randomized patients undergoing arthroscopy of the knee into 3 arms: injection of normal saline (n=49), 0.25% bupivacaine (n=44), or 0.03% morphine (N=46) at the end of the procedure and VAS scores were recorded at times 3, 6, 12, and 24 hours post-operatively. The VAS data were analyzed using analysis of covariance (ANCOVA). VAS was analyzed only for treatment effect in this study. Bupivacaine provided significant postoperative analgesia compared to morphine or saline (where no statistically significant difference was demonstrated). Figure 1 demonstrates the VAS scores for the 3 arms of the study showing that the effect of Intra-articular bupivacaine was noted for all 24 hours of data collection. Additionally, the study found that the time to first supplemental

**Figure 1.** Visual analogue scale (VAS) scores for the three groups who received general anesthesia. The time  $\times$  treatment effect was not statistically significant ( $F = 0.31, P = 0.96$ ) but the treatment effect was significant ( $F = 5.49, P = 0.006$ ). Post-hoc analysis using the Newman-Keuls test showed the bupivacaine group ( $n = 28$ ) to have significantly lower VAS scores than either of the other two groups ( $P < 0.05$ ). There was no difference between the morphine ( $n = 36$ ) and placebo ( $n = 27$ ) groups ( $P = 0.32$ ).

analgesia was increased in both the morphine and bupivacaine arms compared to the placebo.

**c) Specific Aim 2: Determine if patients who undergo hemarthrosis aspiration and intra-articular bupivacaine injection use less supplemental opioid analgesia.**

a. *Working Hypothesis: Intra-articular aspiration and bupivacaine injection will significantly decrease the patients' use of supplemental opioid analgesia in the early post-injury period.*

**Preliminary Studies 2.1: Intra-Articular Injection of Bupivacaine in Knee-Replacement Operations: Results of Use for Analgesia and for Preemptive Blockade.**

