## **Study Procedures**

We propose to study all tibial plateau fractures treated at LUHS for which we have fracture data, treated with ORIF or treated non-operatively. Patients will be identified based on the classification of their injury, that being tibial plateau fracture; we will seek to sub-classify each patient based on the Shatzker classification of tibial plateau fractures and using OA classification as our prospective study will be based on both tibial plateau fractures as a whole and their sub-classification: lateral tibial plateau fracture without depression (I), lateral tibial plateau fracture with depression (II), compression fracture of the lateral (IIIA) or central (IIIB) tibial plateau, medial tibial plateau fracture (IV), bicondylar tibial plateau fracture (V), and tibial plateau fracture with diaphyseal discontinuity (VI). It is important for our prospective study to classify each fracture pattern as they generally differ in energy of injury and thus may affect pain management or need for narcotic pain medications and also potentially affect functional outcomes. Patient inclusion will be based on agreement to participate using informed consent. Additionally, patients may be excluded from the study if they choose not to consent, are incapacitated on initial presentation, have an emergent condition necessitating either operative management or airway protection or have a history of allergic reaction to local anesthetic injection.

Following consent for participation in the study, patients will be blinded to initial management of the tibial plateau fracture with either: Aspiration of the joint alone, aspiration of the knee joint and injection of 20cc bupivacaine 0.5% with 1:200,000 epinephrine or no injection or aspiration therapy for a control arm. Using the block randomization list, the patient will be randomized at the time of consent for participation. For the sake of consistency, all participating treating physicians (orthopaedic on-call residents) will be trained on Sawbones™ Fully Encased Knee Joint with Patella and Ligaments for a standardized aspiration and injection technique.

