For the patients randomized into the treatment arms, the knee will be held in 15-30\* short of full extension and fully prepped using chlorhexidine wipes in a centrifugal manner. An 18 gauge spinal needle will be introduced into the superolateral aspect of the knee (if the knee is too edematous, an inferolateral or inferomedial approach is appropriate, but requires documentation). Aspirate the knee with 60cc syringe until unable to draw out more fluid and record volume on

given study form. Remove the syringe from the needle connection, leaving the 18 gauge needle in place. Draw up 30cc of 0.5% bupivacaine with 1:200,000 epinephrine (Marcaine) with .18-gauge needle into 2nd 60cc syringe. Place the filled syringe on the 18 gauge needle already in the knee and INJECT. Remove needle-syringe construct and place bandage over injection site.

The patient's initial NRS score will be recorded immediately. Subsequent VAS scores will be recorded at time points 0 (5 minutes after intervention), 2, 4, 6, 8, 12, 24 hours after initial work-up of the patient. Patients treated as an outpatient will record these values themselves (copy of recording form submitted with this application). Patients will be directed to bring the completed form with them to their regular clinic follow-up visit. Additionally, supplemental analgesia requirements will be recorded upon administration and will be converted to morphine equivalent units for analysis (copy of recording form submitted with this application). All patients admitted to the orthopedic service will be placed on morphine PCA (determined dosing by weight of patient). All other patients (those admitted to other services) will have analgesia converted to Opioid Morphine Equivalents (OMEs).

Prospectively: Patients will be blinded to initial management of the tibial plateau fracture with either: Aspiration of the knee joint alone, aspiration of the joint and injection of bupivacaine 0.5% with epinephrine or no injection or aspiration therapy for a control arm. Using the block randomization list, the patient will be randomization at the time of consent for participation. The patient's initial VAS score will be recorded at the time of initial work-up. Subsequent VAS scores will be recorded at time points 2, 4, 6, 8, 12, 24 hours after initial work-up of the patient. Additionally, supplemental analgesia requirements will be recorded upon administration and will be converted to morphine equivalent units for analysis.

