## Risks

Risks associated with aspiration of the knee joint include:

- Pain
- Infection
- Inability to remove any fluid or blood from the joint
- The need to attempt another needle stick to place the needle in the correct position

Risks associated with injection of a local anesthetic in the joint include:

- Pain
- Infection
- Chondrolysis reported in vitro with bovine cartilage; no human studies support this finding.
- There have been no reported incidences of systemic issues associated with a single intra-articular knee injection of any local anesthetic

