### **Statistical Considerations**

Sample sizes of 22, 22, and 22 will be allocated to 3 groups (control, aspiration, and aspiration plus injection) using an equal 1:1:1 block randomized allocation. The null hypothesis is that at 24 hours the mean VAS score for these three groups will be equivalent. Power is computed to reject this null hypothesis. A total sample of 66 subjects achieves 84% power to detect at least one pairwise minimal difference score of 1.60mm using the Tukey-Kramer (Pairwise) multiple comparison test at a 0.05 significance level. An assumption was made to set the common standard deviation of the VAS score within any one group to 1.00mm.

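### The withdrawal rule, read with randomisation at consent, excludes randomised patients and the pain and opioid data already recorded from them

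*Combined protocol and SAP*

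**What the plan says.** The Study Withdrawal/Discontinuation section lets a patient leave at any point in treatment or data collection. It then adds: "If the patient decides to withdraw after consent is given they may do so and will not be included in the study".

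Under Study Procedures, "the patient will be randomized at the time of consent for participation", and the same statement recurs later in that section. Pain is scored repeatedly: "Subsequent VAS scores will be recorded at time points 0 (5 minutes after intervention), 2, 4, 6, 8, 12, 24 hours". Opioid use is recorded at each administration. Outpatients fill in their own form: "Patients will be directed to bring the completed form with them to their regular clinic follow-up visit".

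Statistical Considerations tests the 24-hour time point: "The null hypothesis is that at 24 hours the mean VAS score for these three groups will be equivalent". It defines no analysis set, no rule for data collected before withdrawal and no missing-data method.

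The aims are wider than the 24-hour test. Aim 1 concerns "pain scores for patients with tibial plateau fractures in the first 24 hours following injury". Aim 2 asks whether patients given aspiration and "intra-articular bupivacaine injection use less supplemental opioid analgesia".

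**The concern.** Because randomisation happens at consent, withdrawal after consent is normally withdrawal after randomisation. A rule that such patients are not included removes people from the randomised comparison on the basis of something that happened after allocation. It also removes usable data: a patient who leaves after 12 hours already has most of the pain scores and part of the opioid record that Aims 1 and 2 need.

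The harm depends on who leaves. The documents do not show that withdrawal relates to arm or pain, but there are reasons it might. Patients are said to be blinded, yet no sham procedure is described, so controls can probably infer their arm. Aspiration carries its own listed risks, including pain and "Inability to remove any fluid or blood from the joint". If the controls in most pain leave, the control mean falls and benefit is understated. If the aspirated or injected patients in most pain leave, benefit is overstated.

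**Working it through.** **The plan's own figure.** The plan gives no withdrawal rate or allowance, so there is no stated figure on this point to reproduce. The one related figure is 84% power. With 22 per arm, difference 1.60, SD 1.00 and the Tukey-Kramer critical value 2.400 on 63 df, the noncentrality is 1.60/sqrt(2/22) = 5.31 and pairwise power is 99.8%, not 84%. That mismatch is a separate matter and nothing below depends on it.

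**Inputs from the documents**
- 22 patients per arm, target difference 1.60, SD 1.00 (Statistical Considerations).
- Seven scheduled post-intervention scores: 0, 2, 4, 6, 8, 12 and 24 hours (Study Procedures).

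**Assumptions, not in the documents**
- k = 2 or k = 4 of 22 patients leave one arm between 12 and 24 hours, and none leave the others.
- Those who leave are exactly those with the worst 12-hour pain.
- Scores are normal, with 12-to-24-hour correlation r = 0.5 to 0.7.

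**Step 1: data discarded.** Scheduled scores per arm: 7 x 22 = 154. Each leaver has 6 recorded. For k = 2, 12/154 = 8%; for k = 4, 24/154 = 16%. Study Procedures also prints a schedule without time 0. On that one the loss is 10/132 = 8% or 20/132 = 15%.

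**Step 2: shift in the 12-hour mean.** The full arm has expected mean 0 in SD units, so after removing the k largest the mean is -(sum of the k largest expected order statistics)/(22 - k). For n = 22 the four largest are 1.910, 1.458, 1.188 and 0.985.
- k = 2: -(3.368)/20 = -0.168 SD.
- k = 4: -(5.541)/18 = -0.308 SD.

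These 12-hour scores exist, so the whole shift comes from the exclusion. If instead a latent tendency to withdraw correlates 0.5 with pain, the shifts halve to -0.084 and -0.154 SD.

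**Step 3: shift in the 24-hour mean of those remaining.** This is r times the 12-hour shift.

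| k | r = 0.5 | r = 0.7 | As % of 1.60 at SD 1.00 |
|---|---|---|---|
| 2 | -0.084 | -0.118 | 5% to 7% |
| 4 | -0.154 | -0.215 | 10% to 13% |

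**Step 4: what keeping the recorded scores does.** A model using the 12-hour scores of the leavers adds back slope x (12-hour mean of all 22 minus 12-hour mean of those remaining). For k = 2 and r = 0.5, that is -0.084 + 0.5 x 0.168 = 0. Simulation with three arms of 22 gave residual shifts within about 0.003 SD of zero in all four cells.

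**Step 5: what it cannot do.** If leaving depends on the unrecorded 24-hour pain itself, the 24-hour shift is about -0.17 (k = 2) or -0.31 (k = 4) SD. The model reduces it only to between -0.09 and -0.13, or between -0.16 and -0.24 SD. That remainder is a missing-data problem, present whatever the withdrawal sentence says.

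**The case against.** **Reading.** The paragraph is about participants' rights and mentions neither data nor analysis, so non-inclusion could mean only that participation ends. The consent pages, not available for this review, may say what happens to collected data. It would therefore go too far to infer that the sponsor is known to intend deletion. But the preceding sentence already lets patients stop at any time, so non-inclusion is the new content, and nothing in the available text supports the milder meaning. An analyst following the plan as written would exclude these patients.

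**Unblinding.** A reader might infer that controls know they had no needle. The documents do not establish this: Study Procedures twice says patients are blinded. That controls can probably tell is an inference from the absence of a described sham.

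**Size.** A reader might take 0.308/1.60 = 19% as the effect of this rule on the 24-hour result. It is not. In the illustrated case the -0.31 SD shift is at 12 hours, which the stated hypothesis does not test; at 24 hours it arises only when leaving depends on unrecorded pain, most of which rewording does not cure. The rates are also assumed, and 4 of 22 leaving one arm with none elsewhere is extreme. A simulation of the Tukey-Kramer test with no true difference, selecting leavers on the 24-hour score itself, gave familywise error of 5.9% (2 leave) or 7.5% (4 leave) at latent correlation 0.5. Exact worst-pain selection gave about 9% or 17%. Power for a 1.60 difference stayed at or above 96%. The issue is bias, not power, and is probably modest. This objection stands as a limit on size.

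**Outpatient forms.** A 24-hour score on a form not yet returned is in the patient's hands, so losing it is partly a form-return problem that new wording may not solve. This stands.

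**Remedy.** Multiple imputation with arm-specific shifts would answer the wider missing-data gap, not this defect. It is not needed here.

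**Conclusion.** The concern holds. As written, the plan excludes randomised patients who withdraw, along with their recorded data, and no other provision offsets this. The resulting bias is conditional: it needs withdrawal to relate to both arm and pain, which is plausible but not shown, and it can run either way.

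Under the assumed 2 (4) of 22 worst-pain leavers in one arm, the rule shifts the 12-hour mean by 0.17 (0.31) SD and the 24-hour mean by 0.08 to 0.12 (0.15 to 0.22) SD. The 24-hour shift is 5-7% (10-13%) of the target difference at the printed SD, and it is avoidable by keeping the recorded scores. The true size is unknown because the documents give no withdrawal rate. The documents do not support a claim that the trial's result will be materially wrong. They do support changing the rule, because the defect is clear and the change is cheap. The sponsor should make it. Confidence is medium, given the possible milder reading and the unseen consent form.

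**What to change.** Replace the withdrawal sentence with:

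> *A patient may withdraw at any time without consequence. All randomised patients are kept in the arm assigned, and all scores and opioid data collected up to withdrawal are used unless the patient asks that they not be; withdrawals are reported by arm with reasons.*

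Make the consent form consistent with this if it is not already.

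In Statistical Considerations, estimate the 24-hour arm differences from a repeated-measures model using all recorded scores, with Tukey-adjusted pairwise comparisons, so that patients without a 24-hour score still contribute. Do not count an opioid total cut short by withdrawal as a full 24-hour total. A sensitivity analysis for missing 24-hour scores is optional.

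Cost: one paragraph of wording, a check of the consent form and a little more analysis. No extra patients or visits.

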### **Statistical Considerations**

Sample sizes of 22, 22, and 22 will be allocated to 3 groups (control, aspiration, and aspiration plus injection) using an equal 1:1:1 block randomized allocation. The null hypothesis is that at 24 hours the mean VAS score for these three groups will be equivalent. Power is computed to reject this null hypothesis. A total sample of 66 subjects achieves 84% power to detect at least one pairwise minimal difference score of 1.60mm using the Tukey-Kramer (Pairwise) multiple comparison test at a 0.05 significance level. An assumption was made to set the common standard deviation of the VAS score within any one group to 1.00mm.

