#### **Exclusion Criteria:**

- Any Patient that does not wish to participate in the study or is unable to give consent at the initial encounter will be excluded.
- Patients under 18 years old
- Pregnant patients
- Mentally handicapped patients who are unable to give consent

- Incarcerated patients
- Inability or unwillingness to consent for participation
- History of allergic reaction to local anesthetics
- Emergent conditions requiring operations or airway protection
- Polytrauma patients
- Patients presenting for care > 24 hours following their injury.

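### The single stated 24-hour test makes no use of the initial pain score, and the 2 to 12 hour scores are assigned to no analysis

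*Combined protocol and SAP*

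**What the plan says.** Statistical Considerations is the only statistical section. It gives one null hypothesis, "The null hypothesis is that at 24 hours the mean VAS score for these three groups will be equivalent", and one procedure, "using the Tukey-Kramer (Pairwise) multiple comparison test at a 0.05 significance level". It names no covariate, change score, repeated-measures model or summary measure. Analysis of covariance is mentioned only in the account of a cited arthroscopy trial.

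Study Procedures collects more than this test uses:

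- **Initial score.** It is described twice. The first description follows the needle-removal and bandaging steps: "initial NRS score will be recorded immediately. Subsequent VAS scores will be recorded at time points 0 (5 minutes after intervention". The second places it at the initial work-up and calls it a VAS score.
- **Later scores.** These are scheduled at 2, 4, 6, 8, 12 and 24 hours, counted from the initial work-up. Apart from the 24-hour score, none is assigned to an analysis.

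Aim 1 concerns "pain scores for patients with tibial plateau fractures in the first 24 hours following injury", and its working hypothesis is that the intervention "will significantly decrease subjective pain scores in the early post-injury period". The exclusion list removes "Patients presenting for care > 24 hours following their injury", so a patient may enter up to 24 hours after injury.

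**The concern.** Three things are left open.

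1. **Unused baseline.** Pain at presentation is likely to predict pain a day later. Leaving it out gives a wider interval than the collected data allow, and any chance imbalance between arms of 22 goes unadjusted.
2. **Early scores without a role.** The hypothesis is about the early period, but the only tested time is the last one scheduled. With no rule for the five scores from 2 to 12 hours, an early benefit could be claimed from whichever time looks best.
3. **Two clocks.** Aim 1 counts 24 hours from injury. The tested 24 hours has no stated origin, and the only 24-hour score on the schedule is counted from work-up, which comes after injury. Read literally, the tested score falls outside Aim 1's window.

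**Working it through.** **Inputs from Statistical Considerations:** three arms, n = 22 each (N = 66); pairwise difference 1.60; common SD 1.00; Tukey-Kramer at 0.05. **Assumed, because the documents give no value:** the correlation r between initial and 24-hour scores (0, 0.3, 0.5, 0.7) and the correlation between early times (0.3, 0.5, 0.7).

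**Power of the stated test.** The studentized range critical value for 3 groups and 63 df is q = 3.395, equivalent to t = 3.395/√2 = 2.400. The noncentrality for one pair is 1.60/√(2 × 1.00²/22) = 5.31. The noncentral t gives rejection power of 99.8%. The plan states 84%, which is not the rejection power for a single pair at these inputs. Nothing below depends on that figure.

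**Half-width of the Tukey interval, unadjusted.** q × SD/√n = 3.395 × 1.00/√22 = 0.724.

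**Half-width with baseline adjustment.** One covariate leaves 62 df (q = 3.396). The residual variance is multiplied by 1 − r². Chance baseline imbalance multiplies the variance of a difference by about 1 + 1/61 on average, where 61 = 63 − 2. The half-width is therefore 3.396 × √[(1 − r²)/22] × √(1 + 1/61):

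| r (assumed) | √(1 − r²) | Half-width | Change from 0.724 |
|---|---|---|---|
| 0 | 1.000 | 0.730 | 0.9% wider |
| 0.3 | 0.954 | 0.696 | 4% narrower |
| 0.5 | 0.866 | 0.632 | 13% narrower |
| 0.7 | 0.714 | 0.521 | 28% narrower |

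**Early scores.** Suppose there is no treatment effect and each of the five times from 2 to 12 hours is tested by Tukey at 0.05. Simulation with equal correlation between times (100,000 trials for each value) gives a chance of at least one false positive of about 21%, 19% and 15% at correlations 0.3, 0.5 and 0.7.

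**Timing of the initial score.** Set side by side, one description lists the score after the procedure steps and the other ties it to work-up. ANCOVA needs a covariate that treatment cannot have changed. If the score followed aspiration or injection, it would carry part of the effect, and adjusting for it would remove that part from the 24-hour estimate.

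**The clock.** Time from injury to 24-hour score = time from injury to work-up + 24 hours, which exceeds 24 hours for every patient. The schedule is the same in all arms and patients are randomised, so this does not bias the comparison.

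**The case against.** The strongest reply is that nothing stated is wrong. An unadjusted comparison of randomised arms is valid, the 24-hour time point lies in the plan's own range of interest, and power at the plan's inputs leaves no room for improvement. All of that stands. The covariate is an efficiency gain and does not correct an error.

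Four stronger readings might be inferred, and the documents do not support them.

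- **That the trial needs adjustment to reach adequate power.** At the plan's SD it does not. Larger gains appear only at a larger SD. At an assumed SD of 2.0, for example, single-pair power is 60% unadjusted and roughly 65% to 90% adjusted, but no section gives that SD.
- **That the initial score is taken after the procedure.** The text separates it from the subsequent scores, which begin five minutes after intervention, and its second description places it at work-up. A pre-procedure score is the more natural reading. The wording needs reconciling, but it is not evidence of a biased baseline.
- **That all times must be re-anchored to randomisation because** "the patient will be randomized at the time of consent for participation". The documents do not require this. It would change when the tested score is taken and would affect the form that outpatients complete themselves.
- **That the plan intends five uncorrected early tests.** It states none. The 15% to 21% shows what the silence permits.

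How directly the early scores bear on Aim 1 is also partly a judgement, since the aim itself spans 24 hours and the cited arthroscopy trial found no time-by-treatment interaction (P = 0.96). Even so, collected scores relevant to the hypothesis have no assigned use.

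**Conclusion.** The point holds as a gap in specification. The 24-hour test is unbiased and can stay as the tested comparison. Leaving out the baseline gives up between about 4% and 28% of interval width at assumed correlations of 0.3 to 0.7. If the correlation were zero, adjusting would cost under 1%. The effect on power at the plan's inputs is negligible. The more consequential omission is the lack of any rule for the 2 to 12 hour scores, which leaves room for selective claims with a family-wise error of about 15% to 21% if every time were tested at 0.05. The clock mismatch is a matter of wording only. The size of the precision gain and the error range both rest on correlations that the documents do not supply. It should be fixed, because the change is nearly free and is credible only if made before outcome data are examined.

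**What to change.** 1. Analyse the 24-hour score by ANCOVA with arm and the initial NRS score as covariate, keeping Tukey-adjusted pairwise comparisons. NRS is the scale that the rationale under Aim 1 chooses.
2. Reconcile the two descriptions in Study Procedures so that the covariate is the score taken before any procedure in all arms. Because the third arm is "no injection or aspiration therapy for a control arm", state which moment this means for controls.
3. Analyse the 2, 4, 6, 8 and 12 hour scores with the same baseline adjustment as pre-specified secondary results, labelled supportive. If a confirmatory early claim is wanted, name one early measure in advance with its multiplicity rule.
4. Keep the clock that runs from initial work-up, say so in Statistical Considerations, and reword Aim 1's 24-hour window to match.

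**Cost:** protocol wording and one covariate in the model. The tested time point, the score schedule and the 66 patients are unchanged. If some staff currently take the initial score after the procedure, item 2 is also a small change of practice. Alpha needs dividing, or the claims ordering, only if the sponsor wants a confirmatory early result.

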  - As stated previously, there has been substantial research to support the aspiration of fracture hematoma with intra-capsular injuries as it has been shown to decrease pain in the immediate presentation. There has been no research regarding intra-articular injection of local anesthetics in the acute setting of tibial plateau fractures, though there are several studies showing the efficacy of intra-articular anesthetics following total knee arthroplasty and various knee arthroscopic procedures involving the knee. There exist several methods for collecting subjective pain scores. One of the most common pain assessment tools, and the tool documented most in our institution is the VAS. To truly collect VAS data, one must use a 10cm or 100mm rule and have the patient point or state the area on the ruler than most appropriately depicts their current level of pain. The left most position represented by zero is “no pain” whereas the right most position, represented by 10cm or 100mm, is “maximal pain.” However, this method is infrequently carried out in clinical practice and as such we have chosen to use a validated Numerical Rating Scale (NRS) for pain. NRSs range from 0 to 10 and were validated for emergency department patients. One validation study demonstrated that the verbally administered NRS (0 representing “no pain” and 10 representing “maximal, excruciating pain”) had a strong correlation with the VAS. This suggests that for patients who are asked to quantify their pain on a scale of 0-10 after tibial plateau fractures, the NRS is equivalent to using VAS pain scales but with easier reproducibility among varying clinical team members.

**b) Preliminary studies 1.1: Analgesic Effect of Intraarticular Bupivacaine or Morphine After Arthroscopic Knee Surgery: A Randomized, Prospective, Double-Blind Study.**

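### The only powered outcome is named on two pain scales, and its stated unit (mm) does not belong to the scale the plan chose

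*Combined protocol and SAP*

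**What the plan says.** All references are to the combined protocol and SAP.

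- **Rationale and Specific Aims.** Aim 1 concerns "recorded Numerical Rating Scale (NRS) pain scores for patients with tibial plateau fractures in the first 24 hours following injury". The text under it contrasts the two instruments. For the VAS it says "To truly collect VAS data, one must use a 10cm or 100mm rule", and notes that this is seldom done in routine care. It therefore concludes that "we have chosen to use a validated Numerical Rating Scale (NRS) for pain", adding that "NRSs range from 0 to 10". It ends by saying that, for patients asked to rate pain from 0 to 10, "the NRS is equivalent to using VAS pain scales but with easier reproducibility among varying clinical team members".
- **Study Procedures, first account.** Two instruments appear in consecutive sentences: "initial NRS score will be recorded immediately. Subsequent VAS scores will be recorded at time points 0", with later times up to 24 hours. No unit is given. Outpatients fill in the form themselves.
- **Study Procedures, second account** (the paragraph on the prospective part). The initial score and all later scores are called VAS. Again no unit is given.
- **Statistical Considerations.** The hypothesis is "The null hypothesis is that at 24 hours the mean VAS score for these three groups will be equivalent". The target pairwise difference is 1.60 mm and the assumed common SD is 1.00 mm, with 22 patients per group and 84% power by the Tukey-Kramer test at 0.05. The NRS is not mentioned.

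**The concern.** The plan gives a reason for using the NRS, then states its only powered hypothesis on the instrument it set aside, in a unit that a 0-10 rating does not have. Two things are at stake.

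First, the size of effect the trial is designed to detect cannot be read from the plan. The same figure, 1.60, is a very small or a substantial share of the scale depending on which instrument and unit are meant.

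Second, scores come from different recorders: clinical staff for inpatients, and patients on their own for outpatients. The rationale also says that the VAS is the tool most often documented at the institution. Without one named scale and one set of anchors, 0-10 and 0-100 values could both enter the 24-hour data. That would distort the group means being tested, whether or not baseline is used.

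**Working it through.** **1. The instrument, place by place**

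| Place | Initial score | Later scores | Unit |
|---|---|---|---|
| Aim 1 and its rationale | NRS | NRS | 0-10 points |
| Study Procedures, first account | NRS | VAS | none given |
| Study Procedures, second account | VAS | VAS | none given |
| Statistical Considerations | not mentioned | VAS at 24 hours | mm, on the difference and SD only |

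The first three rows disagree on the initial score. The last three disagree with Aim 1 on the 24-hour score.

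**2. What 1.60 means under each reading**

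- 100 mm line, read in mm: 1.60 / 100 = 1.6% of the scale; the SD is 1.00 / 100 = 1%.
- 0-10 points, or a 10 cm rule read in cm: 1.60 / 10 = 16% of the scale; the SD is 1.00 / 10 = 10%.
- Ratio: 16 / 1.6 = 10.

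An SD of 1% of the scale is implausibly small, which suggests that points or cm were meant. That is an inference; the documents do not say so.

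**3. Does the stated power help to identify the unit?**

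Inputs from Statistical Considerations: 22 per group, difference D = 1.60, SD 1.00, Tukey-Kramer at 0.05. The studentized-range critical value for 3 groups and 66 - 3 = 63 degrees of freedom is q = 3.395.

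- Smallest significant pairwise difference: q × SD / √n = 3.395 × 1.00 / √22 = 0.724.
- Standard error of a difference: √(2/22) = 0.3015.
- Power for one pair: approximately Φ((1.60 - 0.724) / 0.3015) = Φ(2.91) = 99.8%.
- Simulated power (200,000 replicates) to detect at least one truly different pair: 99.98% for means (0, 0, D) and 99.8% for (0, D/2, D).

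The stated 84% is not reproduced. With 22 per group, it would need a standardized difference of about 0.9 to 1.0, that is, an SD of about 1.6 to 1.8 for a difference of 1.60. Power depends only on the ratio 1.60 / 1.00, so it is the same in mm, cm or points. The power figure therefore cannot show which unit was meant, and changing the label cannot correct it.

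**4. What a restated SD could do**

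The documents give no SD for the NRS, so the SDs below are assumptions. Power is for at least one truly different pair, 22 per group.

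| Reading of 1.60 | Assumed SD | Power |
|---|---|---|
| NRS points | 2 | 63% (0, D/2, D) to 76% (0, 0, D) |
| NRS points | 2.5 | 44% to 56% |
| NRS points | 3 | 32% to 40% |
| mm on a 100 mm line | 10 to 30 | about 4% to 7% (0, 0, D) |

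**5. Effect of mixed recording on the 24-hour mean**

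Suppose one patient's score x on the 0-10 scale is entered as 10x from a 100 mm line and not corrected. A 22-patient mean then moves by 9x / 22. This exceeds 1.60 points once x is above 1.60 × 22 / 9 = 3.9. The calculation is conditional: nothing in the documents shows that such entries will occur.

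**The case against.** The best defence is that VAS is only a loose label here. The rationale says the ruler method is seldom used, yet calls the VAS the institution's most documented tool, and it treats the NRS as equivalent to it. On that reading every score is a 0-10 rating and only the name and the mm are wrong. This is plausible, perhaps likely. But the equivalence rests on a reported strong correlation, which does not give two scales a common unit, and the same paragraph distinguishes the two methods. The mm in the power statement is a ruler unit. The text leaves the question open.

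A reader might go further and infer that follow-up is recorded in mm while baseline is in points, so that change from baseline has no meaning. The documents do not support this:

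- No follow-up score carries a unit; mm is attached only to the two power inputs.
- The second account in Study Procedures uses VAS at both baseline and follow-up. The accounts conflict, and a mismatch is not established.
- A 10 cm rule read in cm would give the same 0-10 range as the NRS.
- No stated analysis uses the baseline score; the hypothesis compares 24-hour means.

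It also stands that the recording forms are not in the documents and may already print a single scale, and that relabelling alone leaves the power calculation unchanged. Finally, the plan does not designate a primary pain outcome: its primary objective names pain and narcotic use together. The 24-hour score is simply the only outcome with a hypothesis and a power statement.

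**Conclusion.** The contradiction is real and lies in operative text. Aim 1 and its rationale choose the 0-10 NRS, the two accounts in Study Procedures disagree with each other, and the only powered hypothesis is on the VAS with its inputs in mm. This is more than a slip of terminology, because the target difference is ambiguous by a factor of ten: 1.6% of the scale if mm on a 100 mm line is meant, 16% if points or cm.

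Harm to the 24-hour comparison depends on recorders actually using different scales. The documents neither show nor rule that out. A loss of meaning in change scores is not established and touches no planned analysis.

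The failure of 84% power to follow from 1.60 / 1.00 with 22 per group is a separate defect. It is reported here only because correcting the label will not remove it.

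**What to change.** - In both accounts in Study Procedures, name the 0-10 NRS at every time point, including the initial score, in all three arms. Better still, merge the two accounts into one.
- In Statistical Considerations, state the 24-hour hypothesis on the NRS, and give the target difference and SD in NRS points with the basis for the SD.
- Check that the staff and outpatient recording forms print the same 0-10 scale with the same anchors.

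The direct cost is protocol wording and a form check. There may be an indirect cost: once the SD is stated in NRS points with a source, the power for 22 per group may be less favourable than stated (32% to 76% under the assumed SDs of 2 to 3 points), and the sample size may need another look. The power calculation needs its own correction in any case.
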